Procedure	W0 D1 V2	W2 D15 (± 3 d) V3	W4 D29 (± 3 d) V4	W8 D57 (± 3 d) V5	W12 D85 (± 3 d) V6 (EOT) ^a	Notes
RF	X		X	X	X	
hsCRP	X	X	X	X	X	Collected as central laboratory assessment.
Pregnancy Test (serum or urine)	X		X	X	X	WOCBP only. Must have negative pregnancy test within 24 hours prior to the start of treatment.
TBNK	X	X	X		X	
Serum IgM, IgG, IgA, IgE, free Kappa/Lambda light chains	X		X		X	
PK Assessments						
Standard blood samples for the PK assessment of branebrutinib ^d	X		X	X		Refer to Section RA 8.5, RA Table 9 for details.
Blood samples at preselected sites for the PK assessment of branebrutinib and	X			X		Refer to Section RA 8.5, RA Table 9 for details.
metabolites ^e Blood samples for the PK						Refer to Section RA 8.5, RA Table 9 for details.
assessment of concomitant	X		X			Refer to Section RA 6.3, RA Table 9 for details.
medications f						
Blood sample for the PK assessment of abatacept ^g					X	Predose only (sample is not required, if Week 12 is a subject's EOT visit).

RA Table 2 Procedural Outline Branebrutinib Study IM014029 (Week 0 to Week 12)

Procedure	W0 D1 V2	W2 D15 (± 3 d) V3	W4 D29 (± 3 d) V4	W8 D57 (± 3 d) V5	W12 D85 (± 3 d) V6 (EOT) ^a	Notes
Biomarkers						
			-			
Study Treatment						
Randomize	X					

RA Table 2 Procedural Outline Branebrutinib Study IM014029 (Week 0 to Week 12)

Procedure	W0 D1 V2	W2 D15 (± 3 d) V3	W4 D29 (± 3 d) V4	W8 D57 (± 3 d) V5	W12 D85 (± 3 d) V6 (EOT) ^a	Notes
Dispense/Administer Study Treatment	X	X	X	X	X ^{j, k}	Note: At Week 2 the subject is requested to bring IP to the site visit and IP is administered at the site; no new kit is dispensed at this visit.
Study Treatment Compliance		X	X	X	X	

ACR = American College of Rheumatology; AE = adverse event;

; BP = blood

pressure; BTK = Bruton's tyrosine kinase; CDAI = Clinical Disease Activity Index;

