hsCRP	X	X	X	X	X	Collected as central laboratory assessment.
TBNK	X	X		X	X	
Serum IgM, IgG, IgA, IgE, free Kappa/Lambda light chains		X		X	X	
Pregnancy Test (serum or urine)		X	X	X	X	WOCBP.
Immunogenicity (abatacept)	X	X	X	X	X	
PK Assessments					T	
Blood samples for the PK assessment of abatacept	X	X	X	X	X	Refer to Section RA 8.5, RA Table 10
Biomarker Sampling		_			_	

Protocol Amendment No.: 04

Date: 01-Dec-2021

RA Table 3 Procedural Outline Branebrutinib Study IM014029: Open-label Abatacept Therapy (Week 14 to Week 28)

Procedure	Week 14 D99 (± 3 d) V7	Week 16 D113 (± 3 d) V8	Week 20 D141 (± 3 d) V9	Week 24 D169 (± 3 d) V10 (EOT) ^a	Week 28 D197 (±3 d) V11 Safety FU	Notes
Study Treatment						
Dispense/Administer Study Treatment	X	X	X			At Week 14 the subject is requested to bring IP to the site visit and IP is administered at the site; no new kit is dispensed at this visit. No IP administered or dispensed at Week 24.
Study Treatment Compliance	X	X	X	X	X ^f	

; ACR = American College of Rheumatology; AE = adverse event;

DNA = deoxyribonucleic acid; CDAI = Clinical Disease Activity Index;

; DAS28 = Disease Activity Score 28; ECG = electrocardiogram; eGFR = estimated glomerular filtration rate;

TBNK = T cells, B cells, natural killer cells;

EQ-5D-5L = Euro Quality of Life 5 Dimensions Questionnaire: 5-Level version; ESR = erythrocyte sedimentation rate; ET = early termination; FU = follow-up;

HAQ-DI = Health Assessment Questionnaire Disability Index; hsCRP = high-sensitivity C-reactive protein; Ig = immunoglobulin; IP = investigational product; MRI = magnetic resonance imaging; PGA = Physician Global Assessment; PK = pharmacokinetic; PROMIS = Patient-Reported Outcomes Measurement Information System; RAMRIS = Rheumatoid Arthritis Magnetic Resonance Imaging Scoring System;

RF = rheumatoid factor; RNA = ribonucleic acid; SAE = serious adverse event; SDAI = Simplified Disease Activity Index;

SGA = Subject Global Assessment; V = visit; WOCBP = women of childbearing potential.

...... 1

Protocol Amendment No.: 04

Date: 01-Dec-2021

Approved v2.0 930168072 2.0

^c ESR laboratory samples should be collected and recorded by an unblinded staff member who does not perform/have access to other subject procedures, including joint counts. All ESR laboratory samples after screening should be collected and recorded in a blinded fashion. (Refer to RA 8.4.5).

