At the time of the screening visit, the investigative site will access the enrollment option of the IRT system for assignment of a subject number after written informed consent is obtained and before any study-related procedures are performed. This number is assigned sequentially by the system and will be unique across all sites. If a potential subject is rescreened, a new identification number will be used.

Randomized schedules will be generated by the IRT vendor.

Stratification will not be employed.

Before the study is initiated, each investigator will receive log-in information and directions on how to access the IRT. Study treatment will be dispensed at the study visits as listed in the SoA (Section RA 1.3).

RA 6.3 Blinding

Blinded treatment assignments will be managed using IRT. All capsules (branebrutinib 3 mg and branebrutinib PBO) are identical in appearance. Capsules will be supplied in tamper-evident HDPE bottles with each daily dose made up of either active or PBO capsules (as presented in RA Table 5). Prefilled syringes for abatacept will be supplied in 4-packs (all 4 syringes in each pack will be active abatacept). Investigative site staff, Sponsor and designee personnel, and subjects and their families will remain blinded to treatment assignments.

In addition to the treatment blind, results from potentially unblinding biomarkers, whole blood BTK occupancy and pBTK from the baseline measurements on Day 1 onward will be blinded to the investigator and study personnel involved in the study at both the clinical site and the Sponsor, as required.

Blinding of treatment assignment is critical to the integrity of this clinical study. However, in the event of a medical emergency or pregnancy in an individual subject in which knowledge of the IP is critical to the subject's management, the blind for that subject may be broken by the investigator. The subject's safety takes priority over any other considerations in determining if a treatment assignment should be unblinded.

Before breaking the blind of an individual subject's treatment, the investigator should determine that the unblinded information is necessary, ie, that it will alter the subject's immediate management. In many cases, particularly when the emergency is clearly not related to the IP, the

Protocol Amendment No.: 04

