The investigator will perform all efficacy- and safety-related assessments, except for the 66/68 joint count, which will be performed by an independent joint count assessor who is blinded to all other assessments (eg, safety evaluation, laboratory test assessments, etc). For both the investigator and independent joint count assessor, every effort must be made to ensure that the same individual performs the specified required assessments al all visits across the study for each subject. Visit scheduling must take into account the availability of necessary assessors. Training and instruction will be provided to ensure that joint count assessments are conducted in a standard manner across sites. If the evaluator(s) is unable to complete the evaluation, then a qualified individual with overlapping experience may perform the evaluation. Documentation of the individual performing the evaluation is to be recorded in source documents.

The PI, or sub-investigator designated by the PI and confirmed by the Sponsor, may be a Doctor of Medicine or Doctor of Osteopathy, Physician's Assistant, or Nurse Practitioner with experience in the diagnosis and management of subjects with RA.

All assessments should be performed or administered prior to study drug administration unless otherwise indicated. Assessments are to be conducted at approximately the same time of day throughout the duration of the study for a given subject. Assessments conducted on Day 1, Week 0 must be performed per protocol (assessments performed as part of SOC may not be used in lieu of these assessments). Procedures not specified in the protocol that are part of standard care may be performed if they do not interfere with study procedures; any data arising from such procedures are not to be reported in the eCRF.

RA 8.1.1 Patient-reported Outcomes

Patient-reported health outcomes, as studied in RA, include questionnaires and scales that focus on general health, rheumatology, and RA disease-specific issues. The results of these health outcomes will be recorded electronically on eCOA devices provided by the Sponsor or designee to the sites.

RA 8.1.1.1 Health Assessment Questionnaire Disability Index (HAQ-DI)

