In addition to a complete physical examination and medical history to evaluate exposure to TB, all subjects will have a screening test, an IGRA (eg, QuantiFERON®-TB Gold) performed centrally. A subject with an indeterminate IGRA test result from the central laboratory must be retested for confirmation. If the second result is again indeterminate, the subject will be excluded from the study, unless there is documentation of a local negative TB Spot test result. If the second result from the central laboratory is positive, the subject should be considered as having LTBI provided there are no signs or symptoms of active TB. If the second result is negative, the subject may be eligible provided no other exclusion criteria for TB are met. A chest x-ray is also required if one has not been performed within 6 months of screening; a copy of the radiology report must be on file and reviewed by the investigator. If unable to obtain central laboratory results, an IGRA test could be obtained locally, after consultation with the

RA 8.4.5 Clinical Safety Laboratory Assessments

A central laboratory will perform assessments of safety laboratory assessments (except urine pregnancy tests and ESR) and provide reference ranges and laboratory reports. Investigators must document their reviews of each laboratory safety report. Any laboratory test result that the

investigator considers clinically relevant is to be recorded on the appropriate AE page of the eCRF (Section RA 8.2.7).

ESR laboratory samples should be collected and recorded by an unblinded staff member who does not perform/have access to other subject procedures, including joint counts. All samples after screening should be collected and recorded in a blinded fashion.

Additional safety assessments may be performed at local laboratories at the investigator's discretion. The laboratory parameters to be assessed are included in RA Table 8.

In addition, serum or urine pregnancy testing will be performed for WOCBP.

RA Table 8 Clinical Safety Laboratory Assessments

KA Table 6 Chincal Salety Laborat	tory rassessments
Hematology	
Hemoglobin	
Hematocrit	
Total leukocyte count, including manual differential	
Platelet count	
Red blood cell count	
Prothrombin time/INR	
PTT	
aPTT	
Serum Chemistry	
Aspartate aminotransferase	Total Protein
Alanine aminotransferase	Albumin
Gamma glutamyltransferase	Sodium
hsCRP	Potassium
Total bilirubin	Chloride
Direct bilirubin	Calcium
Alkaline phosphatase	Phosphorus

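### RA sub-protocol: nothing withholds post-baseline hsCRP from the investigator who scores the PGA, although ESR is recorded blind

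*Combined protocol and SAP*

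**What the plan says.** **ESR.** RA 8.4.5 and the ESR footnotes to RA Tables 1 to 3 say ESR samples should be "collected and recorded by an unblinded staff member who does not perform/have access to other subject procedures, including joint counts". The footnotes to RA Tables 1 and 3 add: "All ESR laboratory samples after screening should be collected and recorded in a blinded fashion".

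**hsCRP.** RA 8.4.5 states: "A central laboratory will perform assessments of safety laboratory assessments (except urine pregnancy tests and ESR) and provide reference ranges and laboratory reports". It continues: "The laboratory parameters to be assessed are included in RA Table 8". RA Table 8 lists hsCRP under serum chemistry. On the reports, the rule is: "Investigators must document their reviews of each laboratory safety report". RA Table 2 schedules hsCRP at Day 1 and Weeks 2, 4, 8 and 12, on its own row, with the note "Collected as central laboratory assessment".

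**Who rates what.** RA 8.1 says: "The investigator will perform all efficacy- and safety-related assessments, except for the 66/68 joint count". The joint count goes to an independent assessor who is blinded to the other assessments, laboratory tests included. RA Table 2 has the investigator score the PGA at Day 1 and Weeks 2, 4, 8 and 12.

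**What is masked.** RA 6.3 names two laboratory results: "whole blood BTK occupancy and pBTK from the baseline measurements on Day 1 onward will be blinded to the investigator". hsCRP is not named.

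**Endpoint.** Under RA 8.1.3, ACR50 needs 50% improvement in both joint counts and in three of five criteria: subject global, PGA, functional ability, pain, and ESR or CRP. RA 9.3.3 names hsCRP as the ACR component. The PGA also enters SDAI and CDAI.

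**The concern.** The PGA is a visual analog rating made by a physician. If the rater can see how another ACR criterion has moved since baseline, the rating may follow it: a falling hsCRP could pull the PGA down, and a flat one could hold it up. The two criteria would then be less separate than the composite supposes.

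This could differ by arm. The synopsis expects BTK inhibition to lower production of pro-inflammatory cytokines. If hsCRP falls more on branebrutinib, visible trends would tend to move the PGA in that arm's favour. The affected endpoints are ACR50 at Week 12 (primary) and ACR20, ACR70, SDAI and CDAI (secondary). The plan already handles ESR blind, and the text reviewed gives no reason for treating hsCRP differently.

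**Working it through.** **1. The route by which hsCRP reaches the PGA rater**

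| Link | Source | ESR | hsCRP |
|---|---|---|---|
| Where run | RA Table 2, RA 8.4.5 | At the site | Central laboratory |
| Excepted from the central safety laboratory | RA 8.4.5 | Yes | No |
| On the safety parameter list | RA Table 8 | Yes, other analyses | Yes, serum chemistry |
| Recorded blind after screening | RA 8.4.5, RA Tables 1 to 3 | Yes | Not stated |
| Named as masked in RA 6.3 | RA 6.3 | No | No |
| Named as ACR component in RA 9.3.3 | RA 9.3.3 | No | Yes |

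The central laboratory issues reports, the investigator must review each one, and that investigator scores the PGA. No text reviewed removes hsCRP from the reports.

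**2. Which values are known at the Week 12 rating**

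The visit order under RA Table 2 puts the PGA at step 3 and laboratory tests at step 4. The Week 12 hsCRP is therefore drawn after the Week 12 PGA. What can be known is Day 1 and Weeks 2, 4 and 8. This assumes that the Week 8 report returns within the four weeks before Week 12; the documents give no turnaround time.

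**3. The plan's own figure for this endpoint**

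RA 9.1 gives 82% power for 60 against 20 subjects, 45% against 15%, at one-sided 5%.

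- Pooled rate = (60 × 0.45 + 20 × 0.15)/80 = 0.375.
- Null SE = √[0.375 × 0.625 × (1/20 + 1/60)] = 0.125.
- Alternative SE = √(0.15 × 0.85/20 + 0.45 × 0.55/60) = 0.1025.
- z = (0.30 − 1.645 × 0.125)/0.1025 = 0.92, so power is 82.2%.

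The figure reproduces. Masking hsCRP changes neither it nor the sample size.

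**4. How often the PGA is decisive**

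Take subjects who meet both joint criteria. The PGA decides ACR50 when exactly two of the other four criteria are met. Let each be met with probability p.

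- Independent criteria: 6p²(1 − p)². At p = 0.5 this is 6 × 0.25 × 0.25 = 0.375. At p = 0.3 or 0.7 it is 6 × 0.09 × 0.49 = 0.265.
- Positively correlated criteria, which are plausible because all four reflect one disease. Assume a beta-binomial with intraclass correlation 0.4, so a + b = 1/0.4 − 1 = 1.5. The probability is 6 × a(a+1)b(b+1)/(1.5 × 2.5 × 3.5 × 4.5), with denominator 59.0625.
  - p = 0.5: a = b = 0.75, giving 6 × 1.3125²/59.0625 = 0.175.
  - p = 0.3: a = 0.45, b = 1.05, giving 6 × 0.6525 × 2.1525/59.0625 = 0.143.

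The values of p and the correlation are assumptions. The result says how often the PGA could matter, not how often sight of hsCRP would change it. For scale, one changed response moves the placebo rate by 1/20 = 5 points and the branebrutinib rate by 1/60 = 1.7 points.

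**The case against.** **hsCRP on the report is an inference.** No sentence says the result is printed there. Its separate schedule row leaves room for a separate, masked transfer. The Master Protocol and Laboratory Manual were not among the text reviewed, and either could contain a masking rule. This stands, and it is why a cross-reference would be enough if such a rule exists. RA 8.4.5 does say that all samples after screening are handled blind, but within its ESR paragraph; the footnotes to RA Tables 1 and 3 confine the rule to ESR.

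**A reader might infer that the Week 12 CRP criterion feeds directly into the Week 12 PGA.** The documents do not support that, because the visit order puts the PGA before the blood draw. Only the earlier trend can be known.

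**A reader might infer that the ESR safeguard is defeated.** That goes too far. RA 8.4.5 gives no purpose for the ESR rule, and the only procedure it names is joint counts. ESR is run on site, so local separation has its own rationale. The joint assessor is shielded from all laboratory results, hsCRP included, and joint counts are compulsory for ACR50.

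**A reader might infer that the blind is broken.** Nothing reviewed says hsCRP reveals the arm, and the capsules are identical. Investigators would see the same kind of information in both arms. If branebrutinib does not change hsCRP, no difference between arms arises by this route.

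**Safety review.** hsCRP is a listed safety test, and RA 8.2.1 treats infections as potential events of interest. Withholding it has a price, so release on request is needed.

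What remains is one subjective component of the primary endpoint whose rater, under the plan as written, can follow another component's trend.

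**Conclusion.** The point holds as a limited masking gap and merits a cheap improvement. The investigator can know hsCRP through Week 8 when rating the Week 12 PGA, while ESR is recorded blind and the joint assessor sees no laboratory results. The exposure is partial knowledge of response, confined to the PGA and the composites that contain it.

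The size of any bias cannot be derived from the documents. The 14% to 38% range is an illustrative rate at which the PGA is decisive among subjects who meet the joint criteria. The share whose result would change is some unknown fraction of that.

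The conclusion assumes that hsCRP appears on the safety report with the rest of RA Table 8, that the Week 8 result is back before Week 12, and that no unseen document withholds it. Bias between arms also requires that treatment moves hsCRP and that raters respond to it.

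**What to change.** In RA 8.4.5 and RA 6.3, state that hsCRP results after Day 1 are omitted from site laboratory reports until the subject's Week 12 efficacy assessments are complete. Allow release to the investigator on request for a clinical event, and log each release. Screening hsCRP stays visible, since eligibility depends on it. RA 8.4.5 also allows extra local tests at the investigator's discretion, so the log should record any local CRP.

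If the Master Protocol or Laboratory Manual already masks post-baseline hsCRP, a cross-reference in RA 8.4.5 is enough.

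The cost is a central-laboratory report setting, two protocol sentences and a release log. Visits, endpoints and sample size do not change. The downside is that investigators must ask for hsCRP when they want it for a suspected infection or other event.

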The concentration of the relevant concomitant medications will be measured using samples collected predose and 2 hours postdose of branebrutinib or placebo on both Day 1 and Day 29 (Week 4; at which point accumulation of branebrutinib and its metabolites is expected to achieve steady-state). Bioanalytical analysis of all relevant concomitant medications will be conducted post-hoc. The doses of the concomitant drugs and the time they are taken, will be carefully recorded at all times (including Day 1 in Week 0 and on Day 29 in Week 4). The doses of concomitant medications will be carefully recorded at all times. Actual and dose-normalized trough concentrations will be listed, summarized, and compared between posttreatment and pretreatment of branebrutinib and PBO separately; other covariates such as MTX use, gender, etc. can be added to the comparison as needed.

Detailed instructions for PK sample collection for the relevant concomitant medications, labeling, processing, storage, shipping, and disposition are provided in the Laboratory Manual. Plasma samples will be analyzed for all relevant concomitant medications by available validated assays. The results of post hoc analyses will not be recorded in the CSR.

[figure not shown]

Protocol Amendment No.: 04

RA 8.7 Health Economics OR Medical Resource Utilization and Health Economics

Health Economics/Medical Resource Utilization and Health Economics parameters will not be evaluated in this study.

RA 9 STATISTICAL CONSIDERATIONS

RA 9.1 Sample Size Determination

Sample size is calculated based on the estimated effect size for the primary endpoint comparison between branebrutinib and PBO treatment groups. The primary endpoint for the RA sub-protocol is the ACR50 response at Week 12.

Estimates for PBO response rates, treatment differences, and common standard deviations were obtained from the published literature. ^{92,93} Sample size justification is provided below for the RA sub-protocol:

Assuming a total sample size of 80 subjects randomized in a blinded fashion at a 3:1 ratio to branebrutinib (60 subjects) or PBO (20 subjects), there will be 82% power to detect a treatment difference of 30% assuming the PBO response rate is 15% in ACR50 at Week 12, given a 1 sided, two-group test of a difference in binomial proportions with a 5% level of significance.

RA 9.2 Populations for Analyses

For purposes of analysis, the following populations are defined:

Population	Description

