Efficacy data will be summarized using the FAS. Data will be summarized using descriptive statistics (n, mean, standard deviation, median, minimum, and maximum), unless otherwise specified, for continuous variables and frequency distributions (counts and percentages) for categorical variables. Efficacy data will be summarized separately for each sub-protocol and with each sub-protocol combined for variables that are similar among the sub-protocols.

Protocol Amendment No.: 04

Approved v2.0 930168072 2.0

For the RA sub-protocol, data through Week 12 will be presented for:

- Branebrutinib
- Branebrutinib PBO

After Week 12, data may be presented for the following treatments for the RA sub-protocol:

- Branebrutinib followed by Abatacept
- PBO followed by Abatacept
- Branebrutinib and PBO followed by Abatacept

Endpoint	Statistical Analysis Methods
	General Analysis Methodology Response rates of branebrutinib compared to PBO for the primary endpoint will be analyzed using a Chi-square test. The 95% CI for each treatment group response rate and the difference in response rate for branebrutinib compared to PBO will be provided. If expected cell counts are not sufficient, then Fisher's exact test will be used. P-values will be provided.
Primary	Supportive Analyses A Bayesian approach combines current study PBO data and PBO data from historical RA studies will be employed. The probability of response rate difference between branebrutinib and PBO greater than 30% will be calculated with derived posterior distribution. Fixed borrowing or dynamic borrowing method will be implemented. Imputation Method Nonresponder imputation will be used for binary endpoints for subjects who discontinue study treatment early, start a protocol-prohibited medication/therapy prior to the specified timepoint, or otherwise have missing endpoint data for the specified timepoint. Other imputation methods may be considered for sensitivity analyses and will be described in the SAP if used.

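### The RA sub-protocol's 82% power is for a one-sided 5% test, but the primary analysis text does not carry that level over; read as the usual two-sided 5% chi-square, power is about 70 to 72%

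*Combined protocol and SAP*

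**What the plan says.** **Sizing.** RA 9.1, repeated in the RA 1.1 synopsis, has subjects "randomized in a blinded fashion at a 3:1 ratio to branebrutinib (60 subjects) or PBO (20 subjects") and says "there will be 82% power to detect a treatment difference of 30" percentage points, "assuming the PBO response rate is 15% in ACR50 at Week 12". The condition attached is "given a 1 sided, two-group test of a difference in binomial proportions with a 5% level of significance".

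**Analysis.** The primary row of the table in RA 9.4.1 says: "Response rates of branebrutinib compared to PBO for the primary endpoint will be analyzed using a Chi-square test". It adds 95% CIs for each response rate and for the difference, a Fisher fallback when expected counts are too small, and p-values. It gives no sidedness, significance level, 90% interval, decision rule or CI method. The synopsis describes the analysis in the same terms.

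**Related text.** Two-sided 95% intervals are written explicitly only for the continuous RA endpoints. pSS 9.4.1 says its p-values are descriptive because that sub-protocol is not powered for significance; RA 9.4.1 has no such statement. RA 9.4.4 describes a Week 12 database lock whose results go to an independent unblinded team for early development planning. RA 9.4 leaves the SAP to be finalised before database lock.

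**The concern.** The power statement and the analysis statement use different conventions. A chi-square p-value is ordinarily compared with 5% without regard to direction, and a 95% interval corresponds to 2.5% in each tail. The sizing test spends the whole 5% in one tail. A reader who takes the 82% from RA 9.1 and then looks for a chi-square p below 0.05 is using a stricter criterion than the one that was powered.

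ACR50 at Week 12 is the only RA comparison with a power claim, and it feeds the Week 12 planning readout. At stake is whether the readers of that result believe the chance of missing the assumed effect is about 18% or nearer 28 to 30%. A band of borderline results would also be called positive under one convention and not under the other. If the choice is left open, it could be made after the data are seen.

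**Working it through.** **Inputs (RA 9.1).** n1 = 60 and n0 = 20. Placebo rate p0 = 0.15. Difference 0.30, so p1 = 0.45. Level 5%, one-sided.

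**Standard errors.**
- Pooled rate: (60 × 0.45 + 20 × 0.15)/80 = 30/80 = 0.375.
- Under no difference: SE0 = √[0.375 × 0.625 × (1/60 + 1/20)] = 0.1250.
- Under the alternative: SE1 = √[0.45 × 0.55/60 + 0.15 × 0.85/20] = 0.1025.

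**Step 1: reproduce the plan's figure.** Power = Φ[(0.30 − z × SE0)/SE1].
- One-sided 5%, z = 1.645: (0.30 − 0.2056)/0.1025 = 0.921, so 82.2%.
- Exact enumeration over all 21 × 61 outcomes gives 82.6%.

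The stated 82% is confirmed.

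**Step 2: same inputs, two-sided 5%.**
- z = 1.960: (0.30 − 0.2450)/0.1025 = 0.537, so 70.4%.
- Exact enumeration of the uncorrected chi-square gives 71.9%.

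On the exact figures the gap is 82.6 − 71.9 = 10.7 points. This is the probability, under the design assumptions, of a result that is positive by the one-sided rule and not by the two-sided rule.

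**Step 3: which results fall in the gap.** Take 3/20 placebo responders. For 21/60 the pooled rate is 24/80 = 0.30, SE0 = √(0.30 × 0.70/15) = 0.1183 and z = 0.20/0.1183 = 1.690. The other rows follow in the same way. The last column is the difference ± 1.96 × unpooled SE.

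| Branebrutinib | Difference | One-sided p | Two-sided chi-square p | Unpooled Wald 95% CI |
|---|---|---|---|---|
| 21/60 | 20.0 points | 0.045 | 0.091 | 0.2% to 39.8% |
| 22/60 | 21.7 points | 0.035 | 0.070 | 1.8% to 41.5% |
| 23/60 | 23.3 points | 0.027 | 0.054 | 3.4% to 43.2% |

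**Step 4: probability that the 95% CI lies above zero (exact enumeration, 45% versus 15%).** Newcombe 71.9%; unpooled Wald 81.1%. The Wald interval gains this by being too narrow. With a true rate of 15% in both arms it lies wholly above zero about 6.4% of the time, against a nominal 2.5%. As the table shows, it can also exclude zero when the two-sided chi-square p exceeds 0.05.

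**Step 5: the Fisher fallback.** The smallest expected count under the design is 20 × 0.375 = 7.5. Taking below 5 as the trigger (an assumption, since the plan gives no threshold), the fallback would be used about 0.5% of the time, and the exact two-sided power remains 71.9%. It plays no part in the point.

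**The case against.** The strongest reply is that nothing in the documents is wrong as written. The 82% is right for the test it names. Nowhere is the primary RA chi-square called two-sided, and the only sidedness given for that comparison is the one-sided 5% in RA 9.1 and RA 1.1. In a 2×2 table the uncorrected chi-square is the square of the pooled z that reproduces 82%, so a one-sided p-value can be read from it once the direction is known. The two sections can therefore be read as consistent, with the 95% CI there for estimation only.

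The reply continues with the interval. The one worked interval for a difference in proportions, in pSS 9.1 (3% to 57% for 50% versus 20% with 30 and 15 subjects), is unpooled Wald: 0.30 ± 1.96 × √(0.25/30 + 0.16/15) = 0.30 ± 0.270. Applied to RA, that method excludes zero about 81% of the time, close to the stated 82%. Finally, this is Phase 2a with no formal decision rule, there is a supportive Bayesian analysis, and the SAP may settle the matter.

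Much of this stands. A reader might infer that RA 9.1 contains an arithmetic error, that the plan commits to a two-sided test, or that any 95% CI brings power down to 70 to 72%. The documents support none of these.

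It does not remove the mismatch. RA 9.4.1 does not repeat the one-sided level, and an unlabelled chi-square p-value will normally be reported and read as two-sided. The Wald route restores the power only through an inflated error rate, and it can contradict the p-value printed beside it. Unlike pSS, RA does not say its p-values are descriptive.

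**Conclusion.** The point holds in a conditional form. The sizing level is not carried into the primary analysis text. If the chi-square p-value is read two-sided at 5%, power is about 70% (approximate) to 72% (exact) instead of 82%, and the chance of missing a true 45% versus 15% difference is about 28 to 30% instead of about 18%. For the 95% CI alone the figure runs from about 72% (Newcombe) to about 81% (unpooled Wald), because the method is not stated.

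This rests on all 80 subjects being analysed (non-responder imputation keeps dropouts in), on the assumed rates, and on a chi-square without continuity correction; a corrected two-sided test would have lower power, 61.6% by exact enumeration. It also rests on the RA text reviewed here: a one-sided level stated elsewhere in the plan would resolve it.

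Should-fix, not must-fix: the design, the sample size and the stated 82% for its named test are unaffected.

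**What to change.** Choose one convention before the Week 12 lock and write it in both places.

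- **(a)** State in RA 9.4.1 and RA 1.1 that the primary ACR50 comparison is one-sided at 5%, report a matching 90% score-type CI for the difference, and label the 95% CI descriptive. The 82% then stands.
- **(b)** Keep the chi-square and 95% CI, call the test two-sided at 5%, and restate the power in RA 9.1 and RA 1.1 as about 70 to 72%.

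Under either option, name a CI method that agrees with the test, so that the interval and the p-value cannot point in different directions, and say whether a continuity correction is used.

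The cost is a sentence or two in the protocol and SAP, with no added subjects. Option (b) shows a less favourable power. Option (a) openly commits the result to a one-sided 5% standard.
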